3.4 Administration: DO NOT ADMINISTER AS AN INTRAVENOUS PUSH OR BOLUS. Infusion and hypersensitivity reactions may occur. Premedication, consisting of acetaminophen and diphenhydramine, should be considered before each infusion of rituximab. Premedication may attenuate infusion-related events. Since transient hypotension may occur during rituximab infusion, consideration should be given to withholding anti-hypertensive medications 12 hours prior to rituximab infusion.

Administration Guidelines for Adult Patient Population

First Infusion: The rituximab solution for infusion should be administered intravenously at an initial rate of 50 mg/hr. Rituximab should not be mixed or diluted with other drugs. If hypersensitivity or infusion-related events do not occur, escalate the infusion rate in

50 mg/hr increments every 30 minutes, to a maximum of 400 mg/hr. Rituximab infusion should be interrupted for severe reactions. In most cases, the infusion can be resumed at a 50% reduction in rate (e.g., from 100mg/hr to 50mg/hr) when symptoms have completely resolved. Most patients who have experienced non-life-threatening infusion-related reactions have been able to complete the full course of rituximab therapy

Subsequent Infusions: If the subject tolerated the first infusion well, subsequent rituximab infusions can be administered at an initial rate of 100 mg/hr, and increased by 100 mg/hr increments at 30-minute intervals, to a maximum of 400 mg/hr as tolerated. If the first infusion was not well tolerated, the guidelines for the first infusion should be followed for the subsequent infusions.

Subsequent Infusions: If hypersensitivity or infusion-related events occurred during the first infusion, subsequent infusions should be administered in the same manner as the first infusion.

If the subject tolerated the first infusion well, subsequent rituximab infusions should be administered intravenously through a dedicated line at an initial rate of 1.0 mg/kg/hr (to maximum of 100 mg/hr) for the first hour. If hypersensitivity or infusion-related events do not occur, the infusion rate will be escalated by 1.0 mg/kg/hr (maximum 100 mg increase per hour) every 30 minutes, to a maximum rate of 400 mg/hr. If a hypersensitivity or infusion related event develops, the infusion should be temporarily slowed or interrupted. The infusion can continue at one half the previous rate upon improvement of patient symptoms.

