5.7.1 Rituximab

No dose reduction of rituximab is allowed. Treatment of infusion-related symptoms with diphenhydramine and acetaminophen is recommended. Additional treatment with bronchodilators or IV saline may be indicated. Epinephrine, antihistamines, and corticosteroids should be available for

immediate use in the event of a hypersensitivity reaction to rituximab (e.g., anaphylaxis). In most cases, the infusion can be resumed at a 50% reduction in rate (e.g., from 100mg/hr to 50mg/hr) when symptoms and laboratory abnormalities have completely resolved.

5.7.2 ABVD dose modification for hematologic toxicity :

Day of Treatment ANC	ABVD dose level
> 1,000 / μ L	0
\leq 1,000 / μ L	Delay treatment until ANC > 1000/ μ L then give filgrastim or peg-filgrastim with subsequent cycles. At the discretion of the treating physician, chemotherapy may be given without delays
< 1,000/ μ L despite growth factor support	At the discretion of the treating physician reduce DTIC by 25%

5.7.3 ABVD dose modification for non-hematologic toxicity (except nausea, vomiting, alopecia, and fatigue):

Grade	ABVD dose level
0-2	0
3	-1 (reduce DTIC by 25%)
4	Remove from study

5.7.4 For suspected or symptomatic bleomycin lung toxicity: Stop bleomycin and treat with steroids as clinically indicated. For patients older than 60 years, patient with smoking history, or those with bulky mediastinal mass, bleomycin may be omitted for the last 2 cycles at the attending physician's discretion.

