- Active HBV infection or hepatitis (Subjects who are carriers of hepatitis B at the time of discontinuation from study treatment will continue to be followed for clinical and laboratory signs of active HBV infection and for signs of hepatitis)
- Severe or life-threatening anaphylaxis or hypersensitivity reaction
- Inability of subject to comply with study requirements
- Determination by the investigator that it is no longer safe for the subject to continue therapy
- Increasing disease, at any time during treatment or of less than PR after a minimum of 6 courses of therapy. Sometimes, a patient's disease will

progress so rapidly that it is appropriate to change therapy after a single course. Patients who are not responding will be considered failures on this regimen and if medically stable will be offered an alternative regimen. Patients who develop unacceptable toxicity should be removed from the study.

- Grade 3 or 4 non-hematologic toxicity that are not predicted by ABVD or R-ABVD (alopecia, nausea/vomiting, neuropathy).
- Patient's refusal to continue therapy.

11.0 STATISTICAL CONSIDERATION:

This is a trial to study the chemotherapy ABVD (Adriamycin, Bleomycin, Vinblastine, and Dacarbazine) with or without rituximab in treating patients with Hodgkin Lymphoma. Patients will be enrolled into the study at the accrual rate of 3 patients per month with an additional thirty-nine months follow-up period.

Objective

The primary objective of the study is to evaluate the efficacy of the combination regimen of rituximab and ABVD chemotherapy (R-ABVD) and ABVD alone measured as event-free survival (EFS).

Sample Size and Power

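### Patients who stop for toxicity are to be removed from the study, with no stated event-free or overall survival follow-up; separately, no text says whether resumption or discontinuation governs after severe rituximab hypersensitivity

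*Combined protocol and SAP*

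**What the plan says.** **Removal for toxicity.** The dose-modification table in 5.7.3 (non-hematologic toxicity other than nausea, vomiting, alopecia and fatigue) has the grade 4 entry "Remove from study". Section 10 says: "Patients who develop unacceptable toxicity should be removed from the study".

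**Follow-up.** Section 8 schedules disease-status visits from the completion of therapy. Section 5.9 likewise ties the follow-up case report forms to patients who have completed therapy. The only follow-up that Section 10 states after an early stop is hepatitis monitoring of hepatitis B carriers.

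**Analysis.** Section 11 (Analysis Plans) applies intention-to-treat to randomized, eligible patients for efficacy. It analyses EFS and overall survival by Kaplan-Meier, log-rank and Cox methods.

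**Rituximab reactions.** For the first infusion, 3.4 says: "Rituximab infusion should be interrupted for severe reactions. In most cases, the infusion can be resumed at a 50% reduction in rate". For later infusions it says: "If hypersensitivity or infusion-related events occurred during the first infusion, subsequent infusions should be administered in the same manner as the first infusion". Section 5.7.1 repeats half-rate resumption straight after naming a "hypersensitivity reaction to rituximab (e.g., anaphylaxis). In most cases, the infusion can be resumed at a 50% reduction in rate". Section 10 lists "Severe or life-threatening anaphylaxis or hypersensitivity reaction" among the criteria for discontinuing therapy.

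**The concern.** An intention-to-treat analysis needs outcomes as well as membership of the analysis set. If a patient leaves the study at a grade 4 toxicity and no disease or survival follow-up is provided, the analyst has only the time up to removal and would ordinarily censor there. Kaplan-Meier and log-rank methods assume that censored patients have the same later risk as those who remain. Patients who stop for serious toxicity may well not. The primary comparison would then mix the treatment effect with the pattern of removals.

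The second issue is one of safety. A severe but non-life-threatening hypersensitivity reaction falls under the guidance that usually permits resumption and also under a discontinuation criterion. Section 3.1 lists bronchospasm and angioedema among these reactions. It also reports deaths within 24 hours of infusion as part of an infusion reaction complex, with nearly all fatal infusion-related events occurring at the first infusion. Infusion staff need a single rule.

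**Working it through.** **1. The plan's own figures (Section 11).** Hazard ratio: ln(0.77)/ln(0.55) = (-0.2614)/(-0.5978) = 0.437, as stated. Events by the Freedman formula: (1.96 + 0.84)² × [(1 + 0.437)/(1 - 0.437)]² ≈ 7.85 × 6.51 ≈ 51.1, rounded up to 52, as stated. Sample size: 2 × 54 = 108, and 108/0.9 = 120, as stated, or 60 per arm. None of these figures is disputed.

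**2. The follow-up texts side by side.**
- 5.7.3 and Section 10 direct removal from the study.
- Section 8 and the post-treatment forms in 5.9 start from completed therapy, which a removed patient does not reach.
- The two-monthly returns in Appendix A concern participation during treatment.
- The serious adverse event period in 12.1 runs through the protocol-defined follow-up, but it covers safety reporting after rituximab exposure, not EFS.
- Section 10 calls non-responding patients failures on the regimen. It says nothing comparable for toxicity.

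No available text provides EFS or survival follow-up for a patient removed for toxicity.

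**3. Bounds on the effect.** Suppose k of an arm's 60 patients are removed near the start and censored, and the rest follow the planned three-year EFS, s (0.77 in Arm A, 0.55 in Arm B). Kaplan-Meier reports about s. Full follow-up would give (1 - k/60)s + (k/60)x, where x is the removed patients' true three-year EFS. The shift is (k/60)(s - x), with x between 0 and 1. The values of k are assumptions.

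| Arm | k | x = 0 | x = 1 |
|---|---|---|---|
| A | 1 | 0.77/60 = +1.28 points | -0.23/60 = -0.38 points |
| A | 3 | +3.85 | -1.15 |
| A | 6 | +7.70 | -2.30 |
| B | 1 | 0.55/60 = +0.92 | -0.45/60 = -0.75 |

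The ends of each range are extreme. If removed Arm A patients instead had the planned ABVD rate (x = 0.55, an assumption), the shift is 0.22/60 = 0.37 points for one removal and (6/60) × 0.22 = 2.2 points for six. If both arms had six removals with the same x, the arm difference would shift by (6/60) × (0.77 - 0.55) = 2.2 points. Later removal narrows all these ranges.

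**4. The reaction rules side by side.** Section 3.4 covers severe reactions and is permissive. Section 5.7.1, which is trial toxicity management, gives resumption with no severity limit. Section 10 stops therapy for severe or life-threatening hypersensitivity. The overlap is severe but non-life-threatening hypersensitivity or anaphylaxis. There is no cross-reference and no grade for severe, and Section 10 does not say whether rituximab alone or the whole regimen stops. No arithmetic applies here.

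**The case against.** **On removal.** The 5.7.3 entry sits in a column of ABVD dose levels, and Section 10 is headed as criteria for stopping therapy, so both phrases may simply mean off treatment. Section 11 specifies intention-to-treat, and nothing says that removed patients are censored. This shows what the authors may have intended, but it does not supply the missing follow-up. Section 10 elsewhere speaks of discontinuing study treatment, so the protocol uses both expressions.

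The 10% drop-out allowance (12 of 120, about six per arm) gives some protection to event numbers. Losing 10% of the 52 events would lower Schoenfeld power only from 0.847 to 0.808. The allowance does not correct bias from selective loss.

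**On hypersensitivity.** Section 3.4 is drug information and says only that infusion can be resumed in most cases, so Section 10 can be read as the specific exception. The anaphylaxis phrase in 5.7.1 concerns having rescue drugs at hand; the link to resumption is that the two sentences are adjacent. Section 10 also lets the investigator stop whenever continuing is unsafe. These points soften the overlap, and no one is obliged to resume. What stands is that no sentence states which rule governs.

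**A further inference that fails.** A reader might take the resume conditions as contradictory: "when symptoms have completely resolved" in 3.4 (first infusion) against "when symptoms and laboratory abnormalities have completely resolved" in 5.7.1. They are not, because 5.7.1 adds a requirement, and following it satisfies both.

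**Conclusion.** The main point holds. Read literally, the removal wording and the follow-up rules do not deliver the outcomes that the intention-to-treat analyses of EFS and overall survival need. It deserves correction because the remedy is cheap and the primary endpoint is exposed. The hypersensitivity point also holds, as a softer matter of precedence that rests on patient safety alone.

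The conclusion has two limits. Sections 5.0 to 5.2 are not in the available text and may address follow-up. EFS events are not defined there either; if removal for toxicity counts as an event, the problem falls away for EFS but remains for overall survival.

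A reader might infer that the trial is biased toward R-ABVD because Arm A carries the added drug. The documents do not support this: they give no removal rates by arm and no outcomes for removed patients, and the bounds run in both directions. Nor do they support a claim of lost power, or a claim that the infusion conflict reaches every severe infusion reaction. Section 10 names only anaphylaxis and hypersensitivity. The shifts of -0.4 to +1.3 points for one Arm A removal and -2.3 to +7.7 points for six are illustrative bounds, not forecasts.

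**What to change.** **Follow-up.**
- In 5.7.3 and Section 10, replace both removal phrases with: *discontinue study treatment; continue EFS and survival follow-up on the Section 8 schedule*.
- Begin Section 8 and the follow-up form rule in 5.9 with: *After completion or early discontinuation of therapy*.

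**Hypersensitivity.**
- In 3.4 and 5.7.1, state that half-rate resumption, and repeating the first-infusion schedule, apply only to reactions below the Section 10 threshold.
- In Section 10, state that a severe or life-threatening hypersensitivity reaction to rituximab permanently stops rituximab, and that ABVD continues if the investigator judges it safe.

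The cost is one protocol amendment touching 3.4, 5.7.1, 5.7.3, 5.9, 8 and 10, plus continued follow-up of a few patients who stop early. No patients are added, and the design figures in Section 11 do not change.

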8.0 FOLLOW UP EVALUATION

After completion of therapy, patients will have follow up evaluation to determine the disease status every 3 months during the first year of follow up, every 4 months during the second year, every 6 months during years 3-5, and once a year thereafter. Follow up evaluation will include physical examination and appropriate blood tests and imaging studies, as clinically indicated.

9.0 CRITERIA FOR RESPONSE:

The Revised Response Criteria for Malignant Lymphoma^[19] will be used as shown in Table-3 :

Response Definitions for Clinical Trials

Response	Definition	Nodal Masses	Spleen, Liver	Bone Marrow
CR	Disappearance of all evidence of disease	(a) FDG-avid or PET positive prior to therapy; mass of any size permitted if PET negative (b) Variably FDG-avid or PET negative; regression to normal size on CT	Not palpable, nodules disappeared	Infiltrate cleared on repeat biopsy; if indeterminate by morphology, immunohistochemistry should be negative
PR	Regression of measurable disease and no new sites	\geq 50% decrease in SPD of up to 6 largest dominant masses; no increase in size of other nodes (a) FDG-avid or PET positive prior to therapy; one or more PET positive at previously involved site (b) Variably FDG-avid or PET negative; regression on CT	\geq 50% decrease in SPD of nodules (for single nodule in greatest transverse diameter); no increase in size of liver or spleen	Irrelevant if positive prior to therapy; cell type should be specified
SD	Failure to attain CR/PR or PD	(a) FDG-avid or PET positive prior to therapy; PET positive at prior sites of disease and no new sites on CT or PET (b) Variably FDG-avid or PET negative; no change in size of previous lesions on CT		
Relapsed disease or PD	Any new lesion or increase by \geq 50% of previously involved sites from nadir	Appearance of a new lesion(s) $>$ 1.5 cm in any axis, \geq 50% increase in SPD of more than one node, or \geq 50% increase in longest diameter of a previously identified node $>$ 1 cm in short axis Lesions PET positive if FDG-avid lymphoma or PET positive prior to therapy	$>$ 50% increase from nadir in the SPD of any previous lesions	New or recurrent involvement

Abbreviations: CR, complete remission; FDG, [¹⁸F]fluorodeoxyglucose; PET, positron emission tomography; CT, computed tomography; PR, partial remission; SPD, sum of the product of the diameters; SD, stable disease; PD, progressive disease.

10.0 CRITERIA FOR DISCONTINUING THERAPY:

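### Sections 5.7.3 and 10 give conflicting actions for unpredicted grade 3 non-haematologic toxicity, and their exception lists differ

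*Combined protocol and SAP*

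**What the plan says.** Section 5.7.3 is titled "ABVD dose modification for non-hematologic toxicity (except nausea, vomiting, alopecia, and fatigue". Its table has three rows. Grades 0 to 2 keep the full dose. Grade 3 goes to dose level −1, defined as a 25% cut in DTIC, and treatment goes on. Grade 4 is "Remove from study".

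Section 10, headed "CRITERIA FOR DISCONTINUING THERAPY", includes this criterion: "Grade 3 or 4 non-hematologic toxicity that are not predicted by ABVD or R-ABVD". A bracket after it names neuropathy, alopecia and nausea or vomiting. The criterion treats grades 3 and 4 alike and applies a test, whether the event was predicted, that 5.7.3 does not use.

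Section 10 also has two general clauses. One lets the investigator stop therapy judged no longer safe. The other says: "Patients who develop unacceptable toxicity should be removed from the study". Neither is tied to a grade or a type of event.

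A separate rule in Section 5.7.4 covers one organ toxicity: "For suspected or symptomatic bleomycin lung toxicity: Stop bleomycin and treat with steroids as clinically indicated". It gives no grade and points to neither of the other two sections. Sections 5.7.3 and 10 do not refer to each other, and nothing states an order of precedence.

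**The concern.** Both sections are operative. A physician facing a grade 3 or 4 non-haematologic event would consult 5.7.3 for the dose and Section 10 for whether to stop. If the two disagree, the action depends on which page is read.

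At stake are patient safety and the amount of treatment delivered: two patients with the same event could be handled differently without either physician departing from the protocol. The protocol has multi-centre procedures (Section 5.9) and lets some patients be treated by local physicians (Section 5.3 and Appendix A), so several people will apply these rules.

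**Working it through.** No formula applies, and the plan gives no figure to reproduce. The check takes each type and grade of event through both rules.

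Inputs: the scope, exception list and grade rows of 5.7.3; the toxicity criterion and general clauses of Section 10.

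One assumption is needed first. The Section 10 bracket is read as naming toxicities that the regimen does predict, although it is placed after the words for unpredicted ones. Section 3 supports this: its doxorubicin profile includes alopecia, nausea and vomiting. What the text leaves open is whether the bracket is a complete list or only examples.

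| Case | Section 5.7.3 | Section 10 toxicity criterion | Result |
|---|---|---|---|
| 1. Grade 3, unpredicted, on neither list | Continue, DTIC cut by 25% | Met: discontinue | Direct conflict |
| 2. Grade 4 neuropathy | Removal | Not met; general clauses may apply | Mismatch |
| 3. Grade 3 or 4 fatigue | Exempt, no action | Met if the bracket is complete; unclear if it gives examples | Depends on reading |
| 4. Grade 4, predicted, on neither list | Removal | Met if the bracket is complete; not met if it gives examples | Depends on reading |
| 5. Grade 4, unpredicted, on neither list | Removal | Met: discontinue | Agree in effect |
| 6. Grade 3 neuropathy | Continue, DTIC cut by 25% | Not met | Agree |
| 7. Grade 3 or 4 alopecia, nausea or vomiting | Exempt | Not met | Agree |

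Count: 1 direct conflict + 1 mismatch + 2 that depend on the reading + 3 agreements = 7.

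The reading of the bracket also sets the width of case 1. Stomatitis is an example: Section 3 lists it for doxorubicin, and it is on neither exception list. If the bracket is complete, grade 3 stomatitis counts as unpredicted and falls into case 1. If the bracket gives examples, stomatitis can count as predicted, and 5.7.3 alone applies. Case 1 exists under both readings; only its breadth changes.

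The actions are also worded differently. The grade 4 row of 5.7.3 takes the patient off the study. The Section 10 heading concerns therapy, yet its clause on unacceptable toxicity again refers to the study. The text does not say whether a patient stopped for toxicity remains in follow-up.

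**The case against.** The strongest reply is that the sections have different scopes: 5.7.3 concerns ABVD dosing and so covers the regimen's own toxicity, while Section 10 covers what the regimen does not predict. On that reading an unpredicted grade 3 event falls under Section 10 alone and case 1 disappears. The reading is reasonable, but 5.7.3 states no such limit, and its grade 4 row makes it a stopping rule as well as a dosing table. It also leaves grade 4 neuropathy unaligned.

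A second reply concerns grade 4 neuropathy itself. Section 10 lists reasons to stop, and falling outside one of them is not an order to continue. The investigator-safety and unacceptable-toxicity clauses can still apply, so following 5.7.3 breaches nothing in Section 10. This stands: case 2 is a mismatch, not a pair of opposite orders. The same holds for case 4. For fatigue, no conflict follows if the bracket only gives examples and fatigue counts as predicted. That stands too.

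A third reply is oversight. Appendix A item 4 requires the coordinating centre's physician to approve dose or schedule changes before they are made, and Section 5.10 provides quarterly calls among principal investigators. Local physicians of that centre's patients therefore do not choose a section alone. This reduces the problem, but the approving physician works from the same two rules, and item 4 does not clearly extend to other participating sites.

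A reader might go further and infer that stopping would differ by arm, because ABVD patients may be treated locally while rituximab must be given at the coordinating centre (Section 5.3, Appendix A item 9). The documents do not support this. Both sections apply to both arms, and nothing shows that the choice of section would follow the arm.

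**Conclusion.** The point holds in a limited form. Sections 5.7.3 and 10 contradict each other for unpredicted grade 3 non-haematologic toxicity on neither exception list. Their exception lists also differ, over neuropathy and fatigue. The consequence is inconsistent stopping of treatment for the same event, which bears on patient safety and dose delivered.

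The size is one direct conflict among the seven cases. The other discrepancies are a mismatch for grade 4 neuropathy and two cases that turn on whether the Section 10 bracket is complete. The documents give no rates for these events, so the number of patients affected cannot be calculated. No sample size, power or alpha figure changes.

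A reader might also infer bias in the EFS comparison. That is not shown. Section 11 analyses efficacy by intention to treat among randomised, eligible patients, so stopping therapy does not by itself remove a patient from the analysis. How removal for toxicity would be counted in EFS is not stated in the available text, which is a reason to make the wording clear but not evidence of an effect.

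The conclusion rests on taking 5.7.3 as written, without an unstated limit to predicted toxicity, and on reading the bracket as naming predicted events.

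**What to change.** The sponsor should reconcile Sections 5.7.3 and 10 so that each grade of non-haematologic toxicity leads to one action, with one exception list used in both places. The text should state whether that list is complete, and each section should refer to the other. The wording for leaving the study and for stopping therapy should be aligned, so that it is clear whether a patient stopped for toxicity is still followed for EFS. It would help to say in the same edit how Section 5.7.4 relates to the common rule. No view is given here on which action or which exception list is right; that is for the sponsor and investigators.

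The cost is a change of protocol wording. The design and the planned analyses are unaffected.
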